2.2 Analysis sets

All below defined analysis sets will be used to analyze data from both the selection phase (part 1) and the expansion phase (part 2).

Full Analysis Set

The Full Analysis Set (FAS) comprises all subjects to whom study treatment has been assigned by randomization. According to the intent to treat principle, subjects will be analyzed according to the treatment they have been assigned to during the randomization procedure regardless of whether or not treatment was administered. This population will be the primary population for efficacy analysis.

Per protocol set (PPS)

Not applicable.

Safety

The Safety Set includes all subjects who received at least one dose of study treatment. Subjects will be analyzed according to the study treatment received, where treatment received is defined as the randomized treatment if the subject took at least one dose of that treatment or the first treatment received if the randomized treatment was never received.

The actual treatment received corresponds to:

- the randomized treatment if patients took at least one dose of that treatment.
- the first treatment received if the randomized treatment was never received

Note: if a patient is assigned to a dose level for instance, PDR001 400 mg and just receives partial infusion of the treatment, the patient will still be analyzed under PDR001 400 mg treatment arm for safety analysis.

Biomarker analysis set

The biomarker analysis set, as it pertains to the secondary objective (Section 10.5.5 of the protocol), consists of all subjects in the safety set with an evaluable baseline tumor biopsy sample and at least one evaluable post-baseline tumor biopsy sample. [REDACTED]

Immunogenicity (IG) analysis sets

The *Immunogenicity prevalence set* includes all subjects in the Full analysis set with a determinant baseline IG sample **or** at least one determinant post-baseline IG sample.

The *Immunogenicity incidence set* includes all subjects in the Immunogenicity prevalence set with a determinant baseline IG sample **and** at least one determinant post-baseline IG sample.

See [Section 2.10.1.1](#) for the definition of *determinant*.

Patient Classification:

Patients may be excluded from the analysis populations defined above based on the protocol deviations entered in the database and/or on specific subject classification rules defined in [Table 2-4](#).

Table 2-4 Subject classification based on protocol deviations and non-PD criteria

Analysis set	Protocol deviations leading to exclusion	Non protocol deviation leading to exclusion
FAS	No written inform consent	Not applicable
Safety set	No written inform consent	No dose of study medication
Biomarker set	No written inform consent	No dose of study medication and no evaluable post-

		baseline tumor biopsy sample
Immunogenicity Prevalence Set	No written informed consent	Not meeting the definition for inclusion in the Immunogenicity Prevalence set
Immunogenicity Incidence Set	No written informed consent	Not meeting the definition for inclusion in the Immunogenicity Incidence set

Withdrawal of Informed Consent

Any data collected in the clinical database after a subject withdraws informed consent from all further participation in the trial, will not be included in the analysis. The date on which a patient withdraws full consent is recorded in the eCRF.

Death events may be used in the analysis if captured from public records (registers), local law and subject informed consent pending.

Additional data for which there is a separate informed consent, e.g. [REDACTED] biomarker etc., collected in the clinical database without having obtained that consent will not be included in the analysis. These data will be excluded by the presence of the appropriate protocol deviation criterion.

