Windows for multiple assessments

In order to summarize performance status (ECOG), [REDACTED] laboratory, and vital signs collected over time (including unscheduled visits), the assessments will be time slotted. The following general rule will be applied in creating the assessment windows: If more than one assessment is done within the same time window, the assessment performed closest to the target date will be used. If 2 assessments within a time window are equidistant from the target date, then the earlier of the 2 assessments will be used. If multiple assessments on the same date then the worst case will be used. Data from all assessments (scheduled and unscheduled), including multiple assessments, will be listed.

Table 2-1 Time window for ECOG PS assessments

Assessment	Target day of assessment	Time Interval
Baseline		≤ Day 1
Cycle 2 Day 1	29	Day 15 to day 42
Cycle 3 Day 1	57	Day 43 to day 70
Cycle 4 Day 1	85	Day 71 to day 98
Cycle k Day 1 (k≥5)	d=(k-1)*28+1	Day d-14 to day d+13
End of Treatment		Assessment taken at the end of treatment visit
30-day safety follow-up	Post treatment study day 30	Assessment taken at the 30-day safety follow-up visit

Table 2-2 Time window for Laboratory assessments

Assessment	Target day of assessment	Time Interval
Baseline		≤ Day 1
Cycle 1 Day 15	15	Day 2 to day 21
Cycle 2 Day 1	29	Day 22 to day 42
Cycle 3 Day 1	57	Day 43 to day 63
Cycle 3 Day 15	71	Day 64 to day 77
Cycle 4 Day 1	85	Day 78 to day 98
Cycle k Day 1 (k≥5)	d=(k-1)*28+1	Day d-14 to day d+13
End of Treatment		Assessment taken at the end of treatment visit
30-day safety follow-up	Post treatment study day 30	Assessment taken at the 30-day safety follow-up visit

Last contact date

The last contact date will be derived for patients not known to have died at the analysis cut-off using the last complete date among the following:

Table 2-3 Last contact date data sources

Source data	Conditions
Date of Randomization	No Condition
Last contact date/last date patient was known to be alive from Survival Follow-up page	Patient status is reported to be alive, lost to follow-up or unknown

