Start/End dates from further antineoplastic therapy	Non-missing medication/procedure term.
Start/End dates from drug administration record	Non-missing dose. Doses of 0 are allowed.
End of treatment date from end of treatment page	No condition.
Tumor (RECIST) assessment date.	Evaluation is marked as 'done'.
Verification for treatment beyond RECIST1.1 PD	At least one non missing parameter value
Laboratory ████ collection dates	Sample collection marked as 'done'.
Vital signs date	At least one non-missing parameter value
Performance Status date	Non-missing performance status
Start/End dates of AE	Non-missing verbatim term

The last contact date is defined as the latest complete date from the above list on or before the data cut-off date. The cut-off date will not be used for last contact date, unless the patient was seen or contacted on that date. No date post cut-off date will be used. Completely imputed dates (e.g. the analysis cut-off date programmatically imputed to replace the missing end date of a dose administration record) will not be used to derive the last contact date. Partial date imputation is allowed for event (death)/censoring is coming from 'Survival information' eCRF.

The last contact date will be used for censoring of patients in the analysis of overall survival.

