2.7.1 Secondary [REDACTED] efficacy endpoints

Progression-Free Survival (PFS)

PFS is defined as the time from the date of randomization to the date of the first documented progression or death due to any cause. PFS will be based on both local investigator and central assessments of tumor assessments and using RECIST 1.1 criteria (see Appendix 2 of the protocol). The primary analysis will be based on FAS and will include all data observed up-to the cut-off date. PFS will be censored at the date of the last adequate tumor assessment if no PFS event is observed prior to the analysis cut-off date or before the start of the new anticancer therapy date, whichever is earlier. (See [Table 2-4 Subject Table 2-13](#) and [Section 2.7.3](#) for additional details regarding censoring rules and determination of date of last adequate tumor assessment). Discontinuation due to disease progression (collected on the ‘End of treatment’ and ‘End of post treatment follow up’ disposition pages) without supporting objective evidence satisfying progression criteria per RECIST 1.1 will not be considered disease progression for PFS derivation. Clinical deterioration will not be considered as a qualifying event for progression.

[figure not shown]
Disease Control Rate (DCR)

DCR is defined as the proportion of patients with a best overall response (BOR) of confirmed CR or PR, or SD lasting 12 weeks or longer, according to RECIST 1.1 criteria. A patient will be considered to have SD for 12 weeks or longer if a SD response is recorded at 11 weeks or later from randomization, allowing for the ± 1 week visit window for tumor assessments. DCR will be calculated using the FAS based on both the local investigator and central tumor assessments.

Overall Survival (OS)

Overall Survival (OS) is defined as the time from date of randomization to date of death due to any cause. A cut-off date will be established for each analysis of OS. All deaths occurring on or before the cut-off date in the FAS will be used in the OS analysis.

If a patient is not known to have died at the time of analysis cut-off, OS will be censored at the date of last contact.

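### After full withdrawal of consent the plan admits register deaths but no matching alive status, so overall survival is biased downward wherever that exception is used

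*SAP*

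**What the plan says.** Four parts of the main SAP bear on this.

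- **Section 2.2, Withdrawal of Informed Consent.** The general rule is exclusion: "Any data collected in the clinical database after a subject withdraws informed consent from all further participation in the trial, will not be included". One exception follows: "Death events may be used in the analysis if captured from public records (registers), local law and subject informed consent pending". There is no counterpart for patients found to be alive.
- **Section 2.7.1, Overall Survival.** "All deaths occurring on or before the cut-off date in the FAS will be used in the OS analysis". For the rest: "If a patient is not known to have died at the time of analysis cut-off, OS will be censored at the date of last contact".
- **Section 2.1.1, Last contact date.** "The last contact date is defined as the latest complete date from the above list on or before the data cut-off date". The list is Table 2-3. Its only dedicated vital-status source is the Survival Follow-up page, accepted when "Patient status is reported to be alive, lost to follow-up or unknown". No public register is listed.
- **Section 2.7.2.** OS is reported per arm as Kaplan-Meier curves, medians and the proportions alive at 4, 6, 8 and 12 months, with no hypothesis test.

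The Arm 1A SAP refers to the main SAP for withdrawal of consent (Section 2.2) and for OS censoring (Section 2.7.3), so the same rules apply there.

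**The concern.** Kaplan-Meier estimation needs the censoring time not to depend on the outcome. Take two patients who fully withdraw on the same day. One later appears in a death register and becomes an event at the death date, staying in the risk set until then. The other survives and is censored at the last contact on or before withdrawal. Which of them keeps contributing time at risk is settled by whether they died.

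At stake are the reported OS medians and landmark proportions of each arm. The distortion grows with the share of patients who fully withdraw and with how completely registers capture their deaths. Neither need be the same across arms.

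**Working it through.** The SAP states no OS assumption, full-withdrawal rate or register coverage, so there is no figure of its own to reproduce. The check is a reading of the rules, an argument for the direction, and a range for the size.

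**1. Reading.** Applying the rules to a patient who has fully withdrawn:

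| Status learned after withdrawal | Rule that applies | OS record |
|---|---|---|
| Dead, from a public register | Exception in 2.2; all deaths counted in 2.7.1 | Event at death date |
| Alive, from a register | Not in Table 2-3; exception covers deaths only | Censored at last contact on or before withdrawal |
| Alive, entered on the Survival Follow-up page | Clinical-database entry after withdrawal, excluded by 2.2 | Same |

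**2. Direction.** The Kaplan-Meier estimate is S(t) = product over death times of (1 − d/n). With complete register capture, the deaths d and their times are the same as under full follow-up. The risk sets n can only be smaller, because surviving withdrawn patients have left. Each factor is therefore no larger, and the curve cannot lie above the full-follow-up curve. No survival distribution has to be assumed.

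A deliberately extreme illustration: 100 patients, cut-off at month 12, 50 dead by then. Twenty withdraw at the start, of whom 10 die and 10 survive.

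- Full follow-up: 50/100 = 50.0% alive.
- Everyone censored at withdrawal: 40/80 = 50.0%.
- SAP rule (10 withdrawn survivors removed, 10 withdrawn deaths kept): 40/90 = 44.4%.

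**3. Size.** All inputs are assumptions: exponential OS with median 12 months, withdrawal unrelated to prognosis and uniform over months 0 to 6, and administrative follow-up of 9 to 21 months. Kaplan-Meier estimates come from large simulated samples. Full follow-up gives 50.0 to 50.1% at 12 months and a median of 12.0 months.

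| Withdrawn while alive | Register capture | 12-month OS, SAP rule | Loss (points) | Median (months) | Loss (months) |
|---|---|---|---|---|---|
| 4% | 50% | 49.6% | 0.4 | 11.9 | 0.1 |
| 4% | 100% | 49.2% | 0.9 | 11.7 | 0.3 |
| 8% | 50% | 49.1% | 0.9 | 11.7 | 0.3 |
| 8% | 100% | 48.3% | 1.8 | 11.4 | 0.6 |
| 17% | 50% | 48.0% | 2.0 | 11.4 | 0.6 |
| 17% | 100% | 46.4% | 3.7 | 10.9 | 1.1 |

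Censoring every withdrawn patient at withdrawal gives 50.0 to 50.1% and 12.0 months in each row, so under these assumptions the symmetric rule has no bias.

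**4. Sensitivity to timing.** Early withdrawal is unfavourable because it leaves more unseen time at risk. With withdrawal at a constant rate instead (5%, 10% or 20% by 12 months), follow-up of 9 to 27 months and the same 12-month median:

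- 5% and 50% capture: 12-month OS 49.7% against 49.9%, a loss of 0.2 points.
- 20% and 100% capture: 47.9% against 50.1%, a loss of 2.2 points; median 11.3 against about 12.0 months.

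The low end is thus 0.2 to 0.4 points depending on timing, taken as about 0.3.

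**The case against.** The strongest reply is that the asymmetry is not written down anywhere. No single sentence says that a withdrawn patient found alive stays censored at withdrawal, and the SAP describes no register search. Section 2.7.3 censors OS at the date the patient was last known alive, and a lawfully obtained alive date could be put on the Survival Follow-up page. This stands in part: the result comes from Sections 2.1.1, 2.2 and 2.7.1 taken together. It does not remove the problem, because Section 2.2 excludes clinical-database entries made after full withdrawal, and that covers such an alive date.

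A reader might infer that the permissive wording on register deaths leaves the sponsor free to choose once the deaths are known. The text does not support that. The permission is qualified by local law and consent, and most naturally means that such deaths are used where that is allowed. A reader might also assume that a register check is already being made, so that alive status is available at no cost. The SAP does not say so.

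The size is also open to challenge. The rule covers only withdrawal from all further participation, which may be rare. Complete register capture is unlikely when use depends on law and consent. Sampling error is larger: around 50% survival, ignoring censoring, the 95% half-width is 1.96 × √(0.25/n), or 14.6 points for n = 45 (the Part 1 maximum per arm) and 9.8 points for n = 100 (Arm 1A). All of this stands and limits the severity. It does not justify keeping a bias in a known direction that wording can remove.

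Finally, absence from a death register does not prove survival, so censoring at the search date could bias OS upward. That is correct and shapes the fix.

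**Conclusion.** The point holds as a minor one. If register deaths after full withdrawal are used, the stated rules credit time after withdrawal only to patients who die, and Kaplan-Meier OS is biased downward, in Arm 1A as well. With complete capture the direction is certain relative to full follow-up. With partial capture it held in every scenario run, all with withdrawal unrelated to prognosis. If withdrawal is related to prognosis, ordinary informative censoring also acts and could offset part of the bias.

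Under the assumed inputs (12-month median, 4 to 17% withdrawn, 50 to 100% capture) the loss is about 0.3 to 3.7 points in 12-month OS and 0.1 to 1.1 months in the median. The upper end needs both early withdrawal and complete capture. With 4 to 8% withdrawn and 50% capture it is about 0.3 to 0.9 points.

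A reader might infer that the trial's conclusions are at risk. They are not: OS is a descriptive secondary endpoint with no planned between-arm test, and the primary test and the go/no-go probability thresholds rest on the response rate.

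**What to change.** State one symmetric rule in main SAP Section 2.2 and Table 2-3 before database lock; Arm 1A then follows by reference. Either of these would do:

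1. **Main OS analysis without later register deaths.** Censor every fully withdrawn patient at the last contact date on or before withdrawal. Show register deaths after withdrawal only in a sensitivity analysis.
2. **Vital status in both directions, where law and consent allow it to be obtained for withdrawn patients.** Count register deaths as events, and censor patients with documented alive status at the earlier of that date and the cut-off. Add the documented vital-status date to Table 2-3 and extend the Section 2.2 exception to it. Do not treat absence from a death register as proof of being alive.

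Reword the exception in Section 2.2 and the sentence on counting all deaths in Section 2.7.1 to match the chosen rule.

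The cost is a few lines of SAP text. Under the first option a few register deaths move to a sensitivity analysis; under the second a few withdrawn patients need a vital-status date.

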2.2.1 Subgroup of interest

Efficacy

The primary efficacy endpoint will be summarized *if there is sufficient number of patients* in the following subgroups:

- Stratification factor (based on randomization data from IRT)
 - LDH (\leq ULN vs. $>$ ULN)
- BRAFV600 mutation status (wild-type vs. mutant)

In addition, if a combination arm is expanded, the following subgroup analysis may also be performed *if there is sufficient number of patients* using all patients randomized within that combination arm:

- Age category (< 65 years, ≥ 65 years)
- ECOG PS (0 vs ≥0)
- PD-L1 expression (positive, negative) where a positive status is defined as having ≥ 1% expression and negative is defined as having <1% expression

No formal statistical test of hypotheses will be performed for the subgroups, only point estimate of the treatment effect and 95%-confidence intervals will be provided (see [Section 2.5.2](#) and [Section 5.4.1](#) for further analysis details). The objective of the efficacy subgroup analysis is to demonstrate homogeneity of treatment effect in the above subgroups, and to identify potential subgroups with differential efficacy. Summary tables will only be performed if at least 10% of patients or 10 patients are present in each subgroup.

Safety

Safety subgroup analyses will use the same method as for the analysis in the overall analysis set. Key safety analyses (e.g. deaths, SAEs, AESIs, AEs leading to discontinuation) will be repeated on safety set in the following subgroups:

- Sex
- Race
- Age category (< 65 years, ≥ 65 years)

The objective for carrying out these subgroup analyses is to identify potential safety issues that may be limited to a subgroup of patients, or safety issues that are more commonly observed in a subgroup of patients. Summary tables will only be performed if at least 10% of patients or 10 patients are present in each subgroup.

2.3 Patient disposition, demographics and other baseline characteristics

The Full Analysis Set (FAS) will be used for all baseline (including disease characteristics) and demographic summaries and listings unless otherwise specified. Summaries will be reported by treatment arm and for all patients and listings will be reported by treatment arm to assess baseline comparability. No inferential statistics will be provided.

Basic demographic and background data

All demographic and baseline disease characteristics data will be summarized and listed by treatment arm. Categorical data (e.g. gender, age groups: <65 and ≥ 65 years, race, ethnicity, etc...) will be summarized by frequency counts and percentages; the number and percentage of patients with missing data will be provided. Continuous data (e.g. age, weight, height, body mass index) will be summarized by descriptive statistics (N, mean, median, standard deviation,

minimum and maximum). BMI (kg/m²) will be calculated as weight[kg] / (height[m]²) using weight at Screening.

Baseline stratification factors

The number (%) of patients in each stratum (LDH (\leq ULN vs. $>$ ULN)) based on data obtained from the IRT system will be summarized overall and by treatment arm for the FAS. Discordances between the stratum recorded in IRT at the time of randomization and the actual stratum recorded in the clinical database through the data collected on eCRF will be cross-tabulated and listed.

Diagnosis and extent of cancer

Summary statistics will be tabulated for diagnosis and extent of cancer. This analysis will include the following: primary site of cancer, details of tumor histology/cytology, histological grade, stage at initial diagnosis, time since initial diagnosis, time from initial diagnosis to first recurrence/progression (in months), time since most recent relapse/progression to randomization (in months), stage at time of study entry, presence/absence of target and non-target lesions, number and type of metastatic sites involved, and number of tumor infiltrating T cells (TIL)). Note: Presence/absence of target and non-target lesions will be based on the data collected on RECIST target/non-target lesion assessment eCRF pages. Metastatic sites will be based on diagnosis page.

Medical history

Medical history and ongoing conditions, including cancer-related conditions and symptoms entered on (e) CRF will be summarized and listed by treatment arm. The summaries will be presented by primary system organ class (SOC), preferred term (PT) and treatment arm. Medical history and current medical conditions will be coded using the Medical Dictionary for Regulatory Activities (MedDRA) terminology. The MedDRA version used for reporting will be specified in the CSR and as a footnote in the applicable tables/listings.

Other

All data collected at baseline such as child bearing potential, [REDACTED] treatment beyond progression informed consent will be listed.

2.3.1 Patient disposition

Enrollment by country and center will be summarized for all screened patients and also by treatment arm using the FAS. The number (%) of randomized patients included in the FAS will be presented overall and by treatment group. The number (%) of screened and not-randomized patients and the reasons for screening failure will also be displayed. The number (%) of patients in the FAS who are still on treatment, who discontinued the study phases and the reason for discontinuation will be presented overall and by treatment group.

The following summaries will be provided (with % based on the total number of FAS patients):

- Number (%) of patients who were randomized (based on data from IRT system)

- Number (%) of patients who were randomized but not treated (based on ‘DAR’ eCRF page not completed for any study treatment component)
- Primary reason for not being treated (based on “End of Treatment Phase Completion” eCRF page)
- Number (%) of patients who were treated (based on ‘DAR’ eCRF pages of each study treatment component completed with non-zero dose administered)
- Number (%) of patients who are still on-treatment (based on the ‘End of Treatment Phase’ page not completed);
- Number (%) of patients who discontinued the study treatment phase (based on the ‘End of Treatment Phase’ page)
- Primary reason for study treatment phase discontinuation (based on the ‘End of Treatment Phase’ page)
- Number (%) of patients who have entered the post-treatment follow-up (based on the ‘End of Treatment Phase’ page);
- Number (%) of patients who have discontinued from the post-treatment follow-up (based on the End of Post-treatment follow-up page);
- Reasons for discontinuation from the post-treatment follow-up (based on End of Post-treatment follow-up page);
- Number (%) of patients who have entered the survival follow-up (based on the ‘End of Treatment Phase’ or ‘End of Post-treatment follow-up’ page).

Protocol deviations

The number (%) of patients in the FAS with any protocol deviation will be tabulated by deviation category (as specified in the study Data Handling Plan) overall and by treatment group for the FAS. Major protocol deviations leading to exclusion from analysis sets will be tabulated separately overall and by treatment group. All protocol deviations will be listed.

Analysis sets

The number (%) of patients in each analysis set (defined in [Section 2.2](#)) will be summarized by treatment group and stratum.

